### **Physiologic**

- **Echocardiographic parameters**

*Presence and severity of mitral regurgitation* will be assessed by measuring the effective regurgitant orifice area (EROA) by both the proximal isovelocity surface area and the quantitative flow methods. If it is not possible to assess MR using these techniques, MR will be assessed by tracing the jet area and normalizing by the left atrial area.

*Mitral valve apparatus* and quantification of valve area will be assessed by evaluating annular shape and motion, tethering angle and tenting area, papillary muscle position and separation, and calculation of mean trans-mitral stenotic gradient by mitral inflow continuous wave Doppler.

*LV size, geometry and function* will be assessed by the following measures: LV dimensions, ejection fraction (biplane Simpson's rule), LV end-systolic volume index using the biplane volumetric method, LV mass, LV sphericity, radial strain, and twist.

*RV size and function* will be assessed by the following measures: tricuspid annular plane systolic excursion (TAPSE), peak systolic velocity, diastolic E and A velocity (by tissue doppler), and fractional area change.

*Left atrial dimension and volume* will be assessed.

	
Intracardiac pressures and hemodynamics, including pulmonary artery pressures and pulmonary capillary wedge pressure will be assessed by Doppler flow studies.
 
Regional Wall Motion (LV function and viability assessment) will be assessed at baseline and again at one year following surgery.
 
Inter-papillary muscle separation (IPMS) is measured as the distance between the centers of the antero-lateral papillary muscle and postero-medial papillary muscle in a short axis echo plane. IPMS will be measured at three locations: papillary muscle tips, mid-body and base. IPMS will be measured in each frame of the cine loop, optimized to obtain at least 20 frames per heart beat. IPMS is reported in diastole, systole and differences between diastole and systole.
 
 
• Cardiac MRI parameters
 
 
Late-Gadolinium enhanced cardiac MRI will be performed on all patients pre-operatively. Standard protocols will be used to obtain 2 and 4 chamber gated images of cardiac chambers.
 
Presence and severity of mitral regurgitation will be measured as (total stroke volume (EDV-ESV)) – (aortic forward ejection (measured using flow encoded MRI imaging at the aortic valve annulus)). Measurements will be obtained using flow encoded MRI at the mitral annular plane as well.
 
LV size, geometry and function will be assessed by the following measures: LV dimensions, ejection fraction (segmenting LV from short axis and rotated long axis images), LV end-systolic volume index using the biplane volumetric method, LV mass, LV sphericity, strain, and twist.
 
Regional Wall Motion (LV function and viability assessment) will be assessed at baseline and again at one year following surgery.
 
Inter-papillary muscle separation (IPMS) is measured as the distance between the centers of the antero-lateral papillary muscle and postero-medial papillary muscle in a short axis echo plane. IPMS will be measured at three locations: papillary muscle tips, mid-body and base. IPMS will be measured in each frame of the cine loop, optimized to obtain at least 20 frames per heart beat. IPMS is reported in diastole, systole and differences between diastole and systole.

--	---

	
Scar burden and localization will be measured using late Gd enhancement in the myocardium, measured using Otsu's method.
 
 
• Quality of life questionnaires The change in quality of life (QOL) from baseline will be measured, using the disease specific Minnesota Living with Heart Failure (MLHF) score, Duke Activity Status Index Questionnaire and EuroQol 5-D measures of health state preference from the individual and societal perspective. The Minnesota Living with Heart Failure Questionnaire is a disease specific instrument that measures the perception of the physical, psychological and social effects of heart failure (HF) and HF treatment on the patient. The Duke Activity Status Index measures a patient's functional capacity. It can be used to get a rough estimate of a patient's peak oxygen uptake. The EuroQoL 5-D is a standardized instrument for measuring health-related quality of life. This questionnaire provides a simple descriptive profile that consists of 5 dimensions. The 5 domains are anxiety/depression, pain/discomfort, usual activities, self-care, and mobility. The instrument also has a self-assessment of health status. (Appendix 3).
 
• Laboratory Tests Blood collection will be performed using standard phlebotomy techniques at the time of the patients visit <math>\pm 7</math> days of the targeted date. The study nurse drawing the blood will label the tube with the patient's specific code. The blood is then centrifuged to separate plasma and serum, and the plasma and serum are snap frozen. The frozen sample is then shipped to the core laboratory designated by the PI. The core laboratory will record every sample received from the study using an electronic tracking system, and the sample will be stored at -80C. When adequate number of samples (60-80) are acquired, multiple biomarker arrays will be run to measure the quantity of the biomarkers in the sample. Some examples of biomarkers include, Brain natriuretic peptide (BNP), MMPs, TIMPs and catecholamine's etc. Samples remaining after all the tests are performed will be banked.
 

--	---

## 10.0 DATA MANAGEMENT

A secure redcap database ([www.redcap.emory.edu](http://www.redcap.emory.edu)) will be used to maintain enrollment records and patient information. Study personnel requiring access will have their own login and password. Access to clinical study information will be based on individual roles and responsibilities. The application provides hierarchical user permission for data entry, viewing and reporting options. Imaging data will be acquired and viewable to investigators on hospital application.

**Confidentiality of patient data:** By removing the patient information and blinding the datasets, the risk of loss of patient data confidentiality is reduced. Through the entire study, secure networks and databases will be used to manage the data, reducing the risk of any confidentiality breaches. However, there is always a risk of cyber-attacks that may compromise confidential data, and if this study is impacted by such a cyber-attack, the patients and the sponsor will be intimated within 10 days of its discovery.

**Quality assurance:** Quality control of all data will occur automatically, based upon the rules described for each field in the software. Whenever a patient is registered into the system, and a specific field is not entered, the software will prompt for a descriptive reason for not entering the data and the principal investigator will receive a form describing the instance. The investigative team will then explore the event appropriately, and make a note of the reasons or rectify accordingly.

**Monitoring:** The research study coordinator will perform a data audit at 6 month intervals and present the report to the principal investigator. Source files obtained from the patient records will be matched against the data entered into the study database. A minimum of patient last name, first name, date of birth, hospital accession number, sex, informed consent, eligibility criteria, date of enrollment, serious and protocol defined adverse events, mortality, heart failure class, 6 minute walk test and QoL questionnaire will be verified. These data will be 100% source verified. All other data collected will be monitored for data completeness and accuracy.

**Regulatory audit:** A regulatory audit will be performed at time intervals that the IRB deems necessary for this study protocol. The Principal Investigator and coordinators will be available as necessary.

## 11.0 ANALYSIS PLAN

**General design issues:** This is an observational, prospective, non-randomized, single center, multiple phase study. Enrolled patients will have clinically significant FMR with either ischemic or non-ischemic cardiomyopathies. 50 patients are recruited to phase 1 (all 50 receiving undersizing mitral annuloplasty), and 90 patients to phase 2 (75 receiving undersizing mitral annuloplasty and 15 receiving undersizing mitral annuloplasty and papillary muscle approximation). In patients

receiving undersizing mitral annuloplasty, the same rigid annuloplasty ring will be used as consistently as possible, and up to two sizes of downsizing will be performed as consistently as possible. In some patients recruited to the study, the surgeon may decide to switch to mitral valve replacement, or may perform a repair and deem it to be a failure and then switch to mitral valve replacement. In either case, the patient will continue to be part of the study, but with follow-up performed only at 12 months.

**Sample size estimation and statistical analysis plan:** The primary objective of this study is to determine the correlation between pre-operative inter-papillary muscle separation and the 6 month and 12 month post-operative FMR grade after undersizing mitral annuloplasty. Pre-operative inter-papillary muscle separation will be measured and is a continuous variable, while the recurrence of FMR will be deemed binary (1: if MR greater than or equal to 2+ severity observed at 12 months; 0: if MR less than or equal to 2+ severity observed at 12 months). An ROC curve analysis will be used to determine the inflection point of inter-papillary muscle separation at which FMR will recur at 12 months after annuloplasty. Sample sizes are based on previously published data, and on ensuring the ability to detect with high probability, a clinically meaningful presumed benefit for patients undergoing mitral valve repair.

Recruitment to the papillary muscle approximation arm is not based on power analysis as it is only a pilot study.

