## 1.0 PROTOCOL SUMMARY

Title	Improving mitral repair for functional mitral regurgitation (IMPROVE-FMR)
Precis	
Functional mitral regurgitation (FMR) can have an adverse impact on the cardiomyopathic left ventricle, by imposing a chronic low-pressure volume overload. Unrepaired FMR increases the risk of congestive heart failure and death. Undersizing mitral annuloplasty (UMA) is the current gold standard for repair of FMR, but its outcomes are poor with 32.6% of patients presenting with clinically significant recurrent FMR at 1 year after the repair, which increases to 58.8% of the patients at 2 years after annuloplasty. Currently, we do not understand why some patients have failure of annuloplasty, while others do not. Lack of mechanistic insights has inhibited an evidence driven approach in optimizing the repairs adequately – resulting in plethora of new sub-valvular techniques, but very few with appropriate scientific justification to be tested in randomized trials.
 
Our team recently performed a retrospective cardiac MRI study in FMR patients and identified that inter-papillary muscle separation (IPMS) is a strong determinant of FMR severity prior to undergoing any repair. Using image-derived computational biomechanical modeling, we reported that when IPMS is elevated, marginal chordal forces restrict parallelization of the leaflet edges and cause higher FMR. We built upon this observation, and performed an ex vivo bench study to demonstrate that IPMS is a strong determinant of repair success as well. In this study, we demonstrated that the MR volume after repair is directly correlated to the pre-operative IPMS. We recently advanced this study further into a chronic swine model, and demonstrated that swine undergoing papillary muscle approximation (PMA) alone or concomitantly with undersizing mitral annuloplasty (UMA), have better valvular function at 3 months after surgery, compared to animals that receive UMA alone. Their valvular kinematics were superior, and so was their ventricular function.
 
In this observational, prospective, non-randomized study in humans with FMR, we seek to investigate the following:
 

• Question 1: Does pre-operative IPMS correlate with the severity of FMR after UMA at 30 days, 6 months and 12 months. We will study this primary objective by conducting pre-operative MRI and echo in patients receiving UMA, and follow them to one year. Secondly, we will use these images from each patient as input to a computational biomechanical model, which will help demonstrate the chordal forces and stresses before repair, after repair and at the follow-up time points. We will recruit a total of 125 patients to this phase of the study.

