	
Rationale: The decision to perform mitral valve surgery could be made during the surgery by the surgeon, and these patients would be suitable for this study, but would not be consented prior to their surgery. Thus, in this registry, we will identify such patients for recruitment into this study, as their first research point isn't until 6 months after their surgery.
 
Step 1) Charts will be screened for patients who underwent surgery for the lesion of interest at Emory, who would otherwise be eligible for this study but were not recruited as it was not known if they will need mitral valve surgery.
 
Step 2) Patients who are still within 6 months (<math>\pm</math> 1 month) after the date of their surgery will be contacted after surgery and the study objective will be explained, verbal consent will be obtained and the date to visit Emory will be provided.
 
Step 3) Written consent will be obtained at their 6 month visit, and steps 9 and 10 described in registry # 1 will be performed.
 
Registry # 3: Retrospectively identified patients, who already underwent the standard of care surgery, and were identified after the procedure is completed, and are suitable for recruitment to the study for their post-operative research.
 
Rationale: Historical review of patients between dates 1/1/2004 to present who have undergone mitral valve surgery who were not previously identified in the study. These patients have not been consented prior to their surgery. The purpose is to increase the study sample size in order to gain statistical power for outcome analysis.
 
Step 1) Charts will be screened for patients who underwent surgery between 1/1/2004 to present for the lesion of interest at Emory, who would otherwise be eligible for this study but were not recruited as it was not known if they will need mitral valve surgery or were not recruited as they may have received the surgery prior to study start date.

Sample size	
140 subjects in total at Emory University.
 
Group 1: 125 patients to receive UMA and followed to 12 months, with interim imaging.
 
Group 2: 15 patients to receive UMA with PMA and followed to 12 months, with interim imaging.

	
It is expected that we will recruit ~25 patients per year.
 
Group 3: patients' medical charts will be queried between 2004 – present, number of subject charts are undetermined/unknown.

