of FMR after annuloplasty. Since high or low are subjective terms, we seek to recruit 125 patients undergoing undersizing mitral annuloplasty (UMA) at our institution and measure their inter-papillary muscle separation before and after the procedure, and study their impact on 12 month outcomes of the repair. We will perform statistical analysis to determine a cut-off value for IPMS that can stratify patients at risk for UMA failure.

Using the patient specific imaging that we obtain from the 125 patients, we will perform comprehensive biomechanical computational modeling to demonstrate and validate that patients below the cut-off value of IPMS have better mitral valve force distribution, vs. those above the cut-off value of IPMS having poor mitral valve force distribution. This data will help validate the cut-off value as a viable technique to stratify patients for UMA.

In the final step of this study, we will demonstrate that those patients with higher IPMS and at risk of UMA failure, may benefit from a concomitant papillary muscle approximation technique. We will recruit 15 patients to a pilot study, in whom IPMS is above the cut off value, and perform papillary muscle approximation (PMS) along with undersizing mitral annuloplasty (UMA). We will investigate the effect of this combination approach on the outcomes at 6 months and 12 months.

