**Registry # 3: Retrospectively identified patients, who already underwent the standard of care surgery, and were identified after the procedure is completed, and are suitable for recruitment to the study for their post-operative research.**

**Rationale:** Historical review of patients between dates 1/1/2004 to present who have undergone mitral valve surgery who were not previously identified in the study. These patients have not been consented prior to their surgery. The purpose is to increase the study sample size in order to gain statistical power for outcome analysis.

Medical charts will be screened for patients who underwent surgery between 1/1/2004 to present for the lesion of interest at Emory, who would otherwise be eligible for this study but were not recruited as it was not known if they will need mitral valve surgery or were not recruited as they may have received the surgery prior to study start date.

Study assignment: 140 patients will be recruited in total, 1) n=125 to undersizing mitral annuloplasty (UMA) and 2) n=15 to undersizing mitral annuloplasty with papillary muscle approximation (UMA+PMA). Selection will be in a non-randomized manner. Under no circumstances will more than the proposed number of patients be recruited to either groups, without prior approval from the institutional IRB and the study sponsor.

Surgical procedures:

[figure not shown]
Intra-operative echo 1: On the day of the surgery, after the patients are sedated, intubated and anesthetized, the cardiac anesthesiologist will perform a standard of care transesophageal echocardiogram.

Surgical procedures:

*Undersizing mitral annuloplasty (Figure A):* Patients undergoing this procedure will receive a commercially available annuloplasty ring of the surgeon's choice. Sutures are placed around the mitral annulus, and the metallic ring is then implanted onto the mitral annulus to reduce it in size.

*Undersizing mitral annuloplasty with papillary muscle approximation (Figure B):* Patients receiving this procedure will undergo undersizing mitral annuloplasty in a manner that is identical to the procedure outlined above. In addition to the ring implantation, one or two 4-0 pledgedet suture are used to draw the two papillary muscle tips together to reduce the IPMS.

After the procedure is complete, the patients are revived from cardiopulmonary bypass and hemodynamic stability is established.

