## 9.0 DEFINITIONS AND MEASUREMENT OF ENDPOINTS

Primary Endpoints:	The primary endpoint of this study is to investigate if pre-operative inter-papillary muscle separation (diastolic, systolic and diastolic-systolic) correlates with FMR severity at 12 months after surgery with UMA and UMA+PMA.
Secondary Endpoints:	
Survival
 
 
• All-cause mortality at discharge, 6 months and 1 year
 
 
Functional Status and Hospitalizations
 
 
• MACE MACE is defined as a non-weighted composite score comprised of the following: 
 
- Death
 
- Stroke
 
- Worsening heart failure (+1 NYHA class)
 
- CHF hospitalization
 
- Mitral valve re-intervention
 
 
 
• NYHA classification Functional status will be assessed by the NYHA classification scale. (Appendix 1)
 
• 6-minute walk test Functional status will also be measured by a 6-minute walk test, which assesses the distance walked (in feet) during the pre-specified time period. The test will be administered by a trained study coordinator. (Appendix 2)
 
• Readmission rates
 

Readmission rate will be calculated for any cause within the first 30 days and for all cause, cardiovascular and heart failure after 30 days following surgery. Classification of readmission as heart failure related requires at least 2 out of the following signs and symptoms of acute decompensated heart failure:

- Dyspnea felt related to HF
- Treatment with intravenous diuretic, vasodilator or inotropic therapy
- X ray evidence of pulmonary edema or pulmonary vascular congestion
- Rales on physical exam
- PCWP or LVEDP > 18mm Hg

All readmissions will be classified by the investigator and adjudicated by the event adjudication committee.

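### Section 11.0 enrols the PMA pilot before the cut-off meant to select it can exist for all 125 UMA patients, and the primary endpoint and primary objective name different populations

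*Combined protocol and SAP*

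**What the plan says.** **Sequence.** Section 1.0 (Precis, Question 1) treats the UMA cohort as a single phase: "We will recruit a total of 125 patients to this phase of the study". Section 3.0 builds on that cohort: "We will perform statistical analysis to determine a cut-off value for IPMS that can stratify patients at risk for UMA failure". It plans to validate the cut-off by modelling in the same 125 patients. As the last step, "We will recruit 15 patients to a pilot study, in whom IPMS is above the cut off value", and these patients receive PMA with UMA.

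Section 11.0 divides enrolment differently: "50 patients are recruited to phase 1 (all 50 receiving undersizing mitral annuloplasty), and 90 patients to phase 2". Phase 2 is then broken down: "90 patients to phase 2 (75 receiving undersizing mitral annuloplasty and 15 receiving undersizing mitral annuloplasty and papillary muscle approximation". The same section bases the cut-off on an ROC analysis of recurrence at 12 months.

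No section says whose data fix the cut-off used for PMA entry, when it is locked, or whether the 15 come last within phase 2. The eligibility lists (1.0 and 7.2) contain no IPMS threshold, and Study assignment (7.2) says only that selection is non-randomized.

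**Population.** Sections 1.0 and 9.0 word the primary endpoint as whether IPMS "correlates with FMR severity at 12 months after surgery with UMA and UMA+PMA". The primary objective in 2.0, the first objective in 1.0 and the primary objective in 11.0 all refer to UMA alone. Section 2.0 makes PMA a secondary objective. No comparator for the PMA patients is named.

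**The concern.** The cut-off has two roles. It is part of the primary objective (2.0), and it is the stated condition for entering the PMA pilot (3.0). If the pilot enrols before the cut-off is complete, a less precise interim value decides who receives the added procedure, and nothing in the plan identifies that value.

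The population matters because PMA patients are chosen for high IPMS and then treated to lower it. If the procedure works, they combine high pre-operative IPMS with low recurrence, which runs against the association that the primary analysis is meant to estimate.

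**Working it through.** **1. Counts.** Section 1.0 gives "140 subjects in total at Emory University". By phase: 50 + 75 + 15 = 140; UMA 50 + 75 = 125; phase 2 75 + 15 = 90. The totals agree. The order is what conflicts.

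**2. Timing.** Inputs: about 25 patients a year (1.0, Sample size) and a 12-month outcome (11.0). Assumed: the rate covers all 140 patients, and accrual is even and runs phase by phase.
- Phase 2 opens at 50/25 = 2.0 years and closes at 140/25 = 5.6 years.
- The 125th UMA patient enrols at 125/25 = 5.0 years at the earliest, so the full 12-month cut-off exists at 5.0 + 1 = 6.0 years at the earliest. If PMA and UMA patients are mixed, it comes later, up to 5.6 + 1 = 6.6 years.
- The 12-month visit may be 90 days early (7.2). Even then the cut-off comes at about 5.0 + 0.75 = 5.75 years, after phase 2 has closed.
- The rate is not decisive. Without a pause in accrual, the first PMA patient follows the 125th UMA patient directly at best, a year before that patient's outcome is due.

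**3. How many UMA patients could inform PMA entry.**
- Phase 1 only, complete at 2.0 + 1 = 3.0 years: 50 patients, 50 × 0.326 = 16.3 recurrences (18.0 at the 36% given in 3.0).
- PMA patients enrolled last, years 5.0 to 5.6: UMA patients enrolled by years 4.0 to 4.6 have 12-month outcomes, that is 25 × 4.0 = 100 to 25 × 4.6 = 115 patients, or about 33 to 37 recurrences at 32.6%.
- All 125: 40.8 recurrences (45.0 at 36%).

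These counts assume no deaths, valve replacements or dropout.

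**4. Precision.** The plan gives no AUC, so 0.70 is assumed. Hanley-McNeil: SE² = [A(1−A) + (n₁−1)(Q₁−A²) + (n₀−1)(Q₂−A²)]/(n₁n₀), with Q₁ = A/(2−A) = 0.538 and Q₂ = 2A²/(1+A) = 0.576.
- 50 patients (16 and 34): SE² = 3.79/544 = 0.00697; 95% half-width 1.96 × 0.083 = 0.16.
- 125 patients (41 and 84): SE² = 9.33/3444 = 0.00271; half-width 1.96 × 0.052 = 0.10.
- For AUC 0.65 to 0.80 and recurrence of 32.6% to 36%: 0.14-0.17 against 0.09-0.11.

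Simulating the empirical Youden cut-off (two unit-variance normal distributions, AUC 0.70, 32.6% recurrence) gives a 95% range from about the 22nd to the 86th percentile of IPMS with 50 patients, and the 28th to the 81st with 125. Apparent J exceeds true J at the chosen cut-off by about 0.15 and 0.09. Measured against the best attainable J, the excess is 0.12 and 0.07.

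**5. Including PMA patients in the primary association.** Same model, with 15 of the 90 phase-2 patients moved to PMA and given an assumed recurrence of 10% to 33%.
- Drawn at random from those above the cut-off: 140-patient AUC about 0.66 to 0.68, against 0.70.
- The 15 highest IPMS values: 0.61 to 0.65.

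Starting from 0.65 or 0.80 gives losses of similar size.

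**6. Comparator.** At the midpoint cut-off, sensitivity and specificity are both 0.645. The share above is 0.326 × 0.645 + 0.674 × 0.355 = 0.45, and UMA recurrence above it is 0.326 × 0.645/0.45 = 0.467. UMA patients above the cut-off number 0.45 × 125 = 56, or 0.45 × 140 − 15 = 48 if the PMA patients are taken from the same pool.

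**The case against.** The strongest reply is that this is a gap in wording. Section 3.0 implies, but never says in one sentence, that all 125 patients set the cut-off. Section 11.0 is compatible with a phase-1 cut-off applied in phase 2 and refined later. The IPMS entry condition appears only in the Background. Accrual could also pause: holding the pilot until year 6.0 would end it at 6.0 + 15/25 = 6.6 years, well within the 20-year study duration. All of this is fair, but none of these arrangements is written down. Registry 3 adds historical charts, but their number is unknown and the plan does not assign them to the cut-off. The endpoint wording could also mean each group separately, since pooling is not stated. That still leaves it in conflict with a UMA-only objective.

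A reader might go further in three ways that the documents do not support:
- **That at most 50 patients can supply the entry cut-off.** Section 11.0 gives no order within phase 2. If the PMA patients come last, 100 to 115 can.
- **That moving patients to PMA damages the UMA analysis by narrowing its IPMS range.** The phase-2 UMA AUC falls to 0.66 only if the 15 highest values are diverted. With random selection above the cut-off it stays at about 0.70, and Section 3.0 asks only for values above the cut-off.
- **That the plan is biased by 14 points against PMA.** The difference 46.7% − 32.6% = 14 points is what a comparison with all UMA patients would cost. The plan specifies no such comparison.

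The PMA group is an unpowered pilot (11.0), which limits the consequences. Step 4 also shows that the cut-off is imprecise even with 125 patients, so settling the sequence does not cure that.

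**Conclusion.** The point holds as two inconsistencies. First, Sections 1.0 and 3.0 place the PMA pilot after a cut-off from 125 UMA patients, while Section 11.0 enrols it alongside 75 of them. With uninterrupted accrual at the stated rate, entry has to rest on an interim cut-off from somewhere between 50 patients (about 16 recurrences, if entry waits for phase 1 to reach 12 months) and about 115. Second, the primary endpoint and the primary objective define different populations. Including the PMA patients would lower the AUC by roughly 0.02 to 0.04 with random selection above the cut-off, or 0.05 to 0.09 if the highest 15 are chosen. The AUC figures depend on the assumed 0.70, the normal model and the assumed PMA recurrence. The textual conflicts do not.

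This should be corrected before analysis, but it does not invalidate the study: the UMA analysis can proceed once its population is fixed.

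**What to change.** - Reconcile Sections 1.0, 3.0 and 11.0 on which patients' data set the cut-off for PMA entry and when it is locked. How patients are chosen for PMA is the investigators' decision, but the plan must describe it in one consistent way. Report any cut-off used before all 125 outcomes are in as provisional, with its interval.
- Amend the primary endpoint in 1.0 and 9.0 so that the primary association and the final cut-off are estimated in UMA patients only, matching 2.0 and 11.0. Apply a bootstrap optimism correction to the cut-off's performance.
- State that PMA outcomes will be described against UMA patients above the same cut-off, not against all UMA patients.

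The cost is protocol and SAP wording, with no extra patients. The drawback is a smaller descriptive comparator: about 48 to 56 UMA patients instead of 125.

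### The protocol does not settle when the UMA+PMA group opens; if it enrols alongside UMA in phase 2, the UMA cut-off analysis is thinned at high IPMS and no correction is planned

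*Combined protocol and SAP*

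**What the plan says.** Section 11.0 (Analysis Plan, general design issues) divides the 140 patients into two phases: "50 patients are recruited to phase 1 (all 50 receiving undersizing mitral annuloplasty", then "90 patients to phase 2 (75 receiving undersizing mitral annuloplasty and 15 receiving undersizing mitral annuloplasty and papillary muscle approximation". It gives counts only. It states no order of enrolment within phase 2, no rule for who receives PMA, and no cohort from which the cut-off comes.

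The rule that links PMA to IPMS is in Section 3.0 (Background): "We will recruit 15 patients to a pilot study, in whom IPMS is above the cut off value". The same paragraph opens with "In the final step of this study, we will demonstrate that those patients with higher IPMS and at risk of UMA failure", and the paragraphs before it derive the cut-off from the 125 UMA patients.

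Section 7.2 (study assignment) adds "Selection will be in a non-randomized manner" and caps both groups: "Under no circumstances will more than the proposed number of patients be recruited to either groups".

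The primary analysis population is described in two ways. Section 11.0 refers to the "12 month post-operative FMR grade after undersizing mitral annuloplasty". Section 9.0 (and the summary in Section 1.0) asks whether IPMS "correlates with FMR severity at 12 months after surgery with UMA and UMA+PMA". Section 11.0 uses an ROC curve to choose the IPMS cut-off for recurrence at 12 months after annuloplasty. No section adjusts that analysis for selection on IPMS.

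**The concern.** Taken with the selection rule in Section 3.0, the phase-2 counts suggest that 75 UMA and 15 UMA+PMA patients come from one stream and are separated by the predictor under study. Every PMA patient would then be a high-IPMS patient who does not enter the UMA group, while low-IPMS patients always stay.

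Sensitivity, specificity and a threshold read off an ROC curve all depend on how IPMS is distributed in the sample. Thinning only the upper end lowers apparent sensitivity and raises apparent specificity. Recruiting to the full 125 does not cure this. The cut-off is a named deliverable (Sections 2.0, 3.0 and 4.0), intended to identify patients at risk of UMA failure, so its operating characteristics should describe patients presenting for UMA, not those left after selection on IPMS.

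**Working it through.** **1. The plan's counts.** 50 + 75 = 125 UMA; 75 + 15 = 90 in phase 2; 50 + 90 = 125 + 15 = 140. They agree. The sample size itself cannot be reproduced, because no alpha, power, target AUC or dropout rate is given.

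**2. Inputs.** From the documents: the counts above and 12-month recurrence of 32.6% (Section 1.0; Section 3.0 gives about 36%). Assumed, because the documents are silent: IPMS standard normal, logistic recurrence risk, AUC about 0.74 (range 0.69-0.79), and a cut-off at the top third of IPMS (range: top quarter to top half). In this base case recurrence above the cut-off is about 0.55.

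**3. Base case by hand, expected counts.**

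No diversion, 125 UMA patients:
- Above the cut-off: 125/3 = 41.7. Recurrences above: 41.7 × 0.55 = 22.9. All recurrences: 125 × 0.326 = 40.75.
- Sensitivity = 22.9/40.75 = 0.56.
- Non-recurrences: 125 − 40.75 = 84.25, of which 41.7 − 22.9 = 18.8 lie above. Specificity = (84.25 − 18.8)/84.25 = 0.78.

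Concurrent phase 2, 15 patients above the cut-off diverted without regard to how high their IPMS is:
- Above the cut-off in phase 2: 90/3 = 30, so 15 stay. Above in all UMA: 50/3 + 15 = 31.7. Recurrences above: 31.7 × 0.55 = 17.4.
- Below the cut-off: 140 × 2/3 = 93.3. Recurrences below: 140 × 0.326 − 46.7 × 0.55 = 45.6 − 25.7 = 20.0.
- Sensitivity = 17.4/(17.4 + 20.0) = 0.47. Recurrence = 37.4/125 = 0.30.
- Specificity = (93.3 − 20.0)/(125 − 37.4) = 0.84.

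Simulation of the same case gives sensitivity 0.56 to 0.46, specificity 0.78 to 0.84 and recurrence 0.33 to 0.30. AUC goes from 0.74 to 0.73, correlation with recurrence from about 0.39 to about 0.37, and recurrence above the cut-off stays at 0.55.

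**4. Sensitivity to the assumptions.** Over AUC 0.69-0.79 and cut-offs from the top quarter to the top half, sensitivity falls 4-15 points, specificity rises 3-7 points, and the Youden cut-off moves down about 0.1-0.2 SD of IPMS. A separate set of runs (1,500 per scenario) at AUC 0.70 and recurrence 32.6% gives:

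| Cut-off | Diversion | Sensitivity | Specificity | AUC | UMA patients above |
|---|---|---|---|---|---|
| Youden (47% above) | none | 0.662 | 0.629 | 0.701 | 58 |
| | 15 at random | 0.602 | 0.687 | 0.700 | 50 |
| | 15 highest | 0.582 | 0.673 | 0.679 | 50 |
| Top 33% | none | 0.517 | 0.763 | 0.704 | 41 |
| | 15 at random | 0.419 | 0.826 | 0.697 | 31 |
| | 15 highest | 0.402 | 0.816 | 0.683 | 31 |
| Top 20% | none | 0.355 | 0.870 | 0.704 | 25 |
| | 15 at random | 0.210 | 0.932 | 0.687 | 14 |
| | 15 highest | 0.205 | 0.929 | 0.683 | 14 |

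**5. Does weighting repair it?** Weight = (all phase-2 patients above the cut-off)/(those above it who stayed in UMA) = 30/15 = 2. Weighted number above: 16.7 + 2 × 15 = 46.7, which is one third of 140. Weighted sensitivity = 25.7/45.6 = 0.56; weighted specificity = (93.3 − 20.0)/(140 − 45.6) = 0.78. Both match the undiverted values. If the highest 15 are taken, this single weight restores only 0.53 and 0.755.

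**6. Sequential reading.** If PMA opens after 125 UMA patients are enrolled, nobody is diverted and there is nothing to correct.

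**The case against.** The strongest objection is that concurrent diversion is nowhere stated. The only text tying PMA to a cut-off is in Section 3.0, which also places PMA last. It is inconsistent to take the selection rule from that paragraph and ignore its timing. This stands: a reader might infer as fact that high-IPMS patients are moved out while UMA is still enrolling, but the documents support only an unresolved order, and the bias is conditional on it.

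A reader might also infer that the UMA analysis loses its high-IPMS patients altogether. It does not. PMA is capped at 15, and in the base case about 32 of 42 UMA patients above the cut-off remain. Diverting every phase-2 patient above the cut-off would be far more damaging (sensitivity 0.66 to 0.34 at AUC 0.70, Youden cut-off), but no section says that happens.

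Nor do the figures support a claim that the primary correlation and AUC are badly distorted. Under random diversion they barely move, and recurrence risk given IPMS is unbiased if selection depends on IPMS alone. The effects on sensitivity and on the cut-off are also modest beside sampling error in a single study: the 0.10 sensitivity loss is about 1.3 sampling SDs (0.10/0.078), and in the base case the Youden cut-off moves about 0.12 SD of IPMS against a run-to-run SD of about 0.33. Still, this is a bias of known direction, with no correction planned.

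Sections 1.0 and 9.0 include UMA+PMA patients in the primary endpoint, so the UMA-only analysis is one of two versions. Pooling is no cure: the patients added back had a further procedure intended to reduce recurrence. Registry 3 adds historical patients for power, but the plan does not say whether they enter the ROC analysis. Finally, the cohort is already restricted by surgical suitability, so the target is patients presenting for UMA under this protocol, not all patients with functional mitral regurgitation.

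**Conclusion.** The point holds in conditional form. Sections 3.0 and 11.0 leave open when PMA enrolment starts and which cohort sets the cut-off, and they need to be reconciled. If phase 2 is concurrent, the upper end of IPMS in the UMA cohort is thinned (about 42 to about 32 patients above a top-third cut-off). Sensitivity at the cut-off then reads about 4-15 points too low, specificity about 3-7 points too high, and the Youden cut-off sits about 0.1-0.2 SD too low. With only 20% of patients above the cut-off, the sensitivity loss is 13-17 points under random diversion.

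These sizes rest on assumed AUC, cut-off and distribution, none of which the documents give; the direction does not depend on the exact values. AUC and correlation are materially affected only if the highest-IPMS patients are the ones taken. If enrolment is sequential, the effect is nil.

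**What to change.** 1. State in Section 11.0, consistently with Section 3.0, when PMA enrolment opens relative to the 125 UMA patients, which cohort sets the cut-off used to select PMA patients, and how allocation above it is decided. If enrolment is sequential, say so; no weighting is then needed.
2. If it is concurrent, record pre-operative IPMS and allocation for every phase-2 patient. IPMS is already measured; the allocation record is hard to rebuild later.
3. In the UMA ROC analysis, weight each phase-2 UMA patient above the allocation cut-off by (all phase-2 patients above it)/(those above it who stayed in UMA). If allocation varies with IPMS above the cut-off, use instead the inverse of a modelled probability of staying in UMA given IPMS.
4. Report the unweighted result and the recurrence risk by IPMS beside it.
5. If no phase-2 patient above the cut-off stays in UMA, no weight exists. Estimate sensitivity, specificity and the cut-off only in UMA patients enrolled before PMA opens.

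Cost: SAP wording, one log field and slightly wider intervals for the weighted estimates. The loss of precision grows with a higher cut-off: the expected weight is 2 at the top third, 22.5/7.5 = 3 at the top quarter and 18/3 = 6 at the top 20%. The fallback in step 5 is less precise still: if PMA opens once the 50 phase-1 patients are enrolled, it rests on about 16 recurrences (50 × 0.326).
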